6.5 Setting

Palliative care is traditionally delivered where ever patients and those important to them are cared for. This includes: acute hospital care, specialist palliative care units and hospices (voluntary and NHS managed), patients own homes/usual place of residence include care and nursing homes and other community settings. All such settings are currently experiencing care of those with COVID-19, and

many have had extensive service reconfigurations, differing across localities, to enable the care of large numbers of those with COVID-19. We plan to collect data in all the main settings where people are receiving such specialist palliative care (either face to face or via a consultation service).

WP 1:

Inclusion criteria: Palliative care and hospice services across the UK and internationally. This will include: voluntary hospices, hospital based palliative care teams, home care/community teams and other services that offer palliative and/or end of life care. The 2019 Atlas from the European Association for Palliative Care (EAPC) lists specialist palliative care services in the UK.(15) Using this and CQC reports of palliative care services and hospices from their inspections we estimate there are 650 hospices and palliative care services relevant to this proposal across the UK. The UK has more palliative care services than most other countries, so therefore we expect the international response will yield a similar number of services. These will be identified via Hospice UK, Marie Curie Care, Sue Ryder Foundation, the directories of hospital based palliative care teams, the EAPC and our personal networks. The umbrella organisations will write to the services for us, with information about the study, and giving the services the link to complete the on-line survey. We will offer all services the opportunity to complete the on-line survey and will aim to include both adult and children's hospices and palliative care services, those in areas with high and low prevalence of COVID-19, and also different socioeconomic characteristics, ethnicity and culture.

Exclusion criteria: not a palliative care/hospice/end of life service, e.g. having no members of staff with specific expertise/training in palliative care.

WP 2:

Services participating in WP1 from the UK, able to collect information on \geq 10 patients in their care. We aim to recruit ~20 services across settings (hospital, community, voluntary hospice), and areas with different cultural/ethnic and socioeconomic diversities.

Outline agreement/interest to participate has already been reached with 26 services across regions in England, Wales and Scotland. This is more than we need, but we anticipate that some services may not be able to collect data in practice, and so would drop out. We will further sample from services responding to the survey in WP1 as required aiming, where possible, for geographical representation across the UK, of those with different proportions of COVID-19 detected, for variety in socio-demographic factors, and in-service provision types.

WP1 is open to palliative care services and hospices across Europe, via our partner the EAPC, and potentially Australian Palliative Care Services. Because of this we have approached the university of the Chief Investigator, King's College London (KCL), for ethical approval for WP1 to allow international data collection. We obtained ethical approval from KCL Research Ethics Committee on the 21st of April 2020 (LRS-19/20-18541) and have launched the WP1 on-line survey. For international data collection in WP1 we are recruiting participating services only via umbrella/gatekeeping organisations (such as EAPC, and potentially national palliative care organisations, such as the German Palliative Care Association) who would email their membership with information about our study and a link to complete the survey. The subsequent qualitative case studies will only be selected from survey respondents in England, but with variability as to *V.4.0 28 October 2020*

IRAS Number: 282824

service provider and region in England as well as survey responses regarding experience of caring for those with COVID-19, those from minority ethnic communities, and their responses to the pandemic.

WP2 is being conducted in collaboration with Australia and New Zealand Rapid collaboration, who are planning an audit collecting some similar but smaller data sets. We will discuss our findings with them. It is already is of interest to colleagues in Germany, Ireland, Italy and Belgium, which would allow for greater international comparison. We propose to use some of the same symptom assessment measures as the Rapid collaboration, to allow our results to be contrasted with theirs, and in the future possible meta-analysis. If these countries are interested in taking part in our study, we will encourage them to seek local / national ethical approvals.

6.6 **Participants**

WP1

Survey Inclusion criteria: Hospice / palliative care medical directors/clinical leads or their nominees, when not available lead nurse or other.

Exclusion criteria: No lead or delegate available.

Case study participant inclusion criteria: Hospice/palliative care medical directors/clinical leads or their nominees (e.g. respondents to the survey), who will then suggest other potential informants within their service which may include other lead clinicians (across different professional backgrounds), service managers, clinical staff or volunteers.

Exclusion criteria: Patients of the service, or their family carers.

WP2

Inclusion criteria: Consecutive patients supported by the participating palliative care services (including remote consultation), with clinically diagnosed and/or test confirmed COVID-19 diagnosis. This will include patients with and without pre-existing progressive conditions.

Exclusion Criteria: Patients who are <18 years old.

6.7 Sample size

Our sample size in this observational study of the 'natural experiment' of services and treatments changing in response to COVID-19 seeks to balance precision, feasibility and speed.

WP1:

Is largely descriptive yielding rich information. The EAPC atlas and CQC reports suggest ~650 services appropriate to this study in the UK. We aim is to reach as many across the UK as possible to complete the survey. A response rate at 60%, yields 390 services, ~130 inpatient hospices, 130 hospital palliative care teams, 130 home care teams. Subgroups of this size (>105) will detect differences with effect sizes of 0.35, using chi squared (p<0.05, df=5, power 80%). We expect a similar level of response from our European and international partners.

For the follow-up qualitative case studies we will sample from these settings against criteria including geographical representation, service innovations, and socio-demographic factors. We aim to complete around 3-5 qualitative case studies, each with around 3-10 participants, depending on service size.

WP2:

Has descriptive and analytic elements. We collect data extracted from clinical records retrospectively, and where possible also record it prospectively on 200 patients in the UK. We plan to collect data on 200 patients. 9-11 patients per service from 20 services, would give us baseline data on 180-220 patients, follow up data on 80-100 (allowing for 50-60% attrition from those who die too quickly to give more than baseline or baseline plus T1, estimate based on audit in one service). 80 patients with follow up data are needed to detect a difference of 5 points on IPOS (SD=6) between two groups (80 percent power, two-sided 0.05 significance level, mean MCID, SD based on previous research).(27, 28) This sample size will also allow us to identify clear subgroups and actual mean and SDs to enable us to develop hypotheses and sample size calculation for the future. Univariate and multivariate regression analyses, accounting for patient casemix and service clustering, will explore the associations between treatments given and patient outcomes (symptom control), as in other observational studies.(29, 30) Following the RAPID model developed and tested in Australia(31, 32), we plan to work across the sampled sites to collect data such that each centre only needs to collect information about a limited number of patients as a minimum, to reduce the burden on individual clinical members of staff. In addition, having a larger number of services (~20) each collecting smaller number of patients (~10) the effects of clustering will be limited, reducing the impact on power.(30, 33, 34)

We anticipate this data collection will be with patients referred to or seen by the palliative care team within each setting, with data collection of up to 4 weeks or until a minimum of 10 patient's data have been collected, whichever occurs soonest. If services wish to collect data on more than 10 patients we will support that up to 20 patients in the first exploratory phase, providing collection does not exceed 4 weeks. We recognise the challenges of collecting data on a complete cohort, missing data, and with expected attrition of 50-60% through to death(35).

6.8 Recruitment

WP1:

We will disseminate information on the survey widely through our institutional websites, social media, working with key collaborators (EAPC, Hospice UK, Marie Curie Care, Sue Ryder Foundation), directories of hospital based palliative care teams and our personal networks.

Case study participant recruitment:

Case study participants will be selected purposively by the research team in conjunction with case study sites, identified as people who are able to give rich data on the phenomena under study. Selection will depend on potential participant role (there may only be one person who fulfils a particular role), and identification as someone who has rich data perhaps by virtue of their

experience within the site in caring for people with COVID-19 and nominated by the key contact within the case study site. They would be asked to distribute invitations to the relevant members of staff who then respond to the research team. Reminders will be sent after two weeks if no response is forthcoming. We anticipate interviewing between 3-10 participants per case study site, depending on the size of the site(s) selected

WP2:

The palliative care clinical team within participating sites will identify patients and facilitate data collection on as complete a cohort as possible of those patients who meet the inclusion criteria across a set time period and to an agreed maximum number of patients. Informed consent from patient participants will not be possible given the illness status of the patients, and the likely rapidly deteriorating health status of those who will form the cohort for this study. Therefore, we will ask the direct care team to access this routinely collected data and de-identify it before transferring these data securely to the research team. There will be no breach of confidentiality as the research team will not receive any confidential patient information.

6.9 Data collection

WP 1:

On line survey using REDCap builds on but considerably extends the Italian survey of palliative care directors(7). REDCap is a secure web application for building and managing online surveys and databases. While REDCap can be used to collect virtually any type of data, it is specifically geared to support online or offline data capture for research studies and similar operations.

Key variables: palliative care services type, location, catchment area, innovations in response to COVID-19, deployment of workforce and volunteers, use of virtual technologies, support for care homes and other settings, bereavement support offered, advance care planning, protocols/recommendations being used for symptom management, challenges, equipment needs, examples of best successes, open comments.

Sites will be encouraged to enter data online directly, but if required they can give the information to a trained interviewer over the telephone or virtual connection (e.g. via Microsoft teams or Zoom) who will enter the data for them. Or they prefer they can be sent the survey as a word document via email to complete and return electronically (e.g. via secure NHS email).

Qualitative case studies involving telephone or video (e.g. using Microsoft Teams, Zoom or similar) interviews with clinical leads of participating services and other nominated informants. The case studies may focus on a specific theme of interest that emerges in the phase I WP1 survey, e.g. use of telecommunications, advance directives, medicines, or on particular services. A topic guide rather than a fixed schedule will guide but not constrain the interviews, ensuring that interviews are driven by participant issues. Interviews will be conversational to aid developing rapport to explore complex and potentially challenging and emotional issues. The topic guide will evolve as categories are

> V.4.0 28 October 2020 IRAS Number: 282824

discovered through the interviews and analysis but are likely to include exploration of the service response to COVID-19, the opportunities and challenges experienced, their perceptions of the impact of COVID-19 on their service, and appraisal of their impact on patients and family carers into bereavement care. Interviews may vary in length, but are likely to be around 30 minutes.

WP2:

Data will be extracted from clinical records retrospectively or collected propectively where possible, for individual patients up to 4 time points at 24-hour intervals, reflecting on the previous 12 hours of care, or until the death of the patient if earlier. We acknowledge the high probability of attrition, missing data and/or missing timepoints given the pandemic situation, and will not exclude the patient from the cohort in this situation. To minimise burden on the direct clinical care team we have used routinely collected data where possible. Baseline is determined as first contact with the palliative care team during the current episode of care. This may be on admission to the care setting, or later in the care trajectory.

Data collection procedures will have to be locally adapted to take account of infection control procedures that may affect the ability to collect certain forms of data (e.g. on paper, in the presence of someone with known infection). Where possible clinical teams will enter data directly using password protected bespoke secure study data base (likely to be REDCap as for the survey and Australian study, but Macro is also being considered). Patients will have a unique alpha-numeric code allocated which will identify both the site providing data and where the patient is in their consecutive sequence.

Data collection has been designed to be parsimonious, in line with current NICE guidance(36), available information on COVID-19 core outcome sets(37), and using validated tools such as the IPOS(38, 39)

Timepoint	Data	Details
BASELINE (T0)	Date and time stamp	
	Setting	ICU, Acute hospital ward, palliative care unit/hospice, emergency department, home, nursing care home, hostel/sheltered accommodation, other (insert details).
	Gender	Male, female, other
	Ethnicity	ONS categories
	Age	Age in years
	Weight/Height	Calculate BMI
	Date of first COVID symptoms	Date
	Date of COVID diagnosis, if known	Date
	Date referred to palliative care	Date
	Postcode	Transform to LSOA to enable linkage to deprivation measure (IMD)

Table 1 Data collection

	Smoking currently	yes/no
	Charlson Comobrbidity Index	MI, CCF, peripheral vascular disease, CVA,
		Dementia, Leukaemia, Cancer, Connective
		Tissue Disease, Diabetes, Hypertension, Renal
		disease, liver disease, peptic ulcer disease,
		COPD, Lymphoma, AIDS.
	Date and time of assessment	Date and Time
	Place of Care	ICU/Acute hospital ward/In-patient
		hospice/palliative care ward in a hospital
		/Community hospital/Emergency department
		/Own home (or of a relative/friend)/Nursing
		home/Care home/Sheltered accommodation/
		Hostel/Community bed (not hospital) /Other
	Australian Modified Karnofsky	Range from 100 (normal) to 10 (comatose or
	Performance Scale	barely rousable).
	Phase of illness	Stable, Fluctuating, Deteriorating, Dying
	Laboratory tests (if available)	D-dimer, Lymphocyte count, Lactic
		Dehydrogenase, High sensitivity C-reactive
		protein
	Oxygen therapy	Room air/O2 via nasal prongs or mask/BiPAP or
		CPAP/ventilated
	IV fluids	Yes, what was received or rate over the last 12
		hours
	Temperature	Celsius
	Baseline symptom severity (over	Breathlessness, fever, cough, pain, shivering,
	the past 12 hours/currently	sore or dry mouth, anxiety, agitation,
	scoring from U (not at all) to 4	confusion/delirium, drowsiness, weakness/lack
	(overwheiming) based on the	of energy, poor appetite, constipation,
	validated IPOS measure (28, 40)	diarrhoea, nausea, vomiting, poor mobility,
	List of surront modications being	Medication symptom indication dose
	List of current medications being	frequency route
	Open comments	
	Communication with family and	Ves how communication was facilitated
	friends	No, why communication could not be
		facilitated
	Particination in other COVID-19	Ves which studies
	studies	
T1/T2		
	Date and time of assessment	Date and Time
	Place of Care	ICU/Acute hospital ward/In-patient
		hospice/palliative care ward in a hospital
		/Community hospital/Emergency department
		/Own home (or of a relative/friend)/Nursing
		home/Care home/Sheltered accommodation/
		Hostel/Community bed (not hospital) /Other
	Australian Modified Karnofsky	Range from 100 (normal) to 10 (comatose or
	Performance Scale	barely rousable).
	Phase of illness	Stable, Fluctuating, Deteriorating, Dying

	Laboratory tests (if available)	D-dimer, Lymphocyte count, Lactic
		Dehydrogenase, High sensitivity C-reactive
		protein
	Oxygen therapy	Room air/O2 via nasal prongs or mask/BiPAP or
		CPAP/ventilated
	IV fluids	Yes, what was received or rate over the last 12
		hours
	Temperature	Celsius
	Symptom severity (over the past	Breathlessness, fever, cough, pain, shivering,
	12 hours/currently scoring from	sore or dry mouth, anxiety, agitation,
	0 (not at all) to 4 (overwhelming)	confusion/delirium, drowsiness, weakness/lack
	based on the validated IPOS	of energy, poor appetite, constipation,
	measure (28, 40)	diarrhoea, nausea, vomiting, poor mobility,
		other.
	Changes made to medications	Medication, symptom indication, dose,
	given to the patient since last	frequency, route.
	assessment	
	Open comments	
	Communication with family and	Yes, how communication was facilitated
	friends	No, why communication could not be
		facilitated
D	Death (De) or discharge (Di)	outcome, whether died or discharged,
		transferred, dates where known
	Place of death or destination on	ICU, Acute hospital ward, palliative care
	discharge	unit/hospice, emergency department, home,
		nursing care home, hostel/sheltered
		accommodation, other.
	Symptoms in 12 hours before	Breathlessness, fever, cough, pain, shivering,
	death or discharge.	sore or dry mouth, anxiety, agitation,
		confusion/delirium, drowsiness, weakness/lack
		of energy, poor appetite, constipation,
		diarrhoea, nausea, vomiting, poor mobility,
		other.
	Changes made to medications	Medication, symptom indication, dose,
	given to the patient since last	frequency, route.
	assessment	
	Free text comment box	

6.10 Data analysis

WP1:

Survey: Descriptive analysis of innovations in services, workforce and volunteer deployment, and their impacts on care and bereavement services; identification of good practice, and sharing of approaches and knowledge. Change in practice, most effective treatments. Bereavement services identified. Hospice and palliative care service characteristics that are associated with most effective changes. How people from different sociodemographic groups and ethnic groups are supported. If

data permit, contingency tables assessed using chi-squared to compare types of responses/challenges/use of technology by key characteristics (e.g. of hospital support teams, services that are NHS or voluntary sector funded).

Qualitative case studies: Data analysis will follow a Framework Analysis approach to facilitate analysis between cases using a matrix approach. Framework analysis facilitates within and cross case pattern matching and has been used in case studies in palliative and end of life care (41-44). The approach involves a systematic process of sifting, charting, and sorting material according to key issues and themes following five key stages: familiarisation, identifying a thematic framework, indexing, charting, and mapping and interpretation. Cross case pattern matching follows to identify thematic factors associated with challenges and successes of the site response to COVID-19 whilst taking account of context. This should provide information on what is working well, and challenges, barriers and strategies for overcoming them. All qualitative analyses will be managed using NVivo™ software.

WP2:

A full statistical analyses plan will be drafted and approved by the study steering committee. Data analysis will be focused on addressing our research aims: describing the characteristics of those receiving palliative care, assessing symptom prevalence at baseline and over time, describing treatments used, and assessing their effect and the outcomes of care.

- a) Transform data: calculate Charlson Comorbidity Index; days since symptoms/diagnosis of COVID-19 before baseline; calculate BMI. Characterise the different groups of patients receiving palliative care (e.g. those who are dying from COVID-19, those with severe pre-existing multimorbidity who are dying with COVID-19, and those previously known to palliative care). Categorise medication according to type and symptom target.
- b) Understanding and description of missing data to inform analysis of missing data and attrition. We will use the MORECare categorisation of missing data and attrition,(35, 45) as well as data missing not at random, missing at random, missing completely at random, to inform any imputation and sensitivity analysis assumptions.
- c) Describe the characteristics of the participant cohort at baseline, and at each timepoint. Continuous/ordinal normally or near normally distributed data will be summarised using means and standard deviations (SD), medians and interquartile ranges (IOR) will be used if non-normally distributed. Total IPOS and subscale scores will be calculated with means and SDs. Categorical data will be described using frequencies and percentages.
- d) Understand effects of clustering by centre, and intra-cluster correlation coefficients (ICC) and how these should be adjusted for the analysis
- e) Changes in scores over time are estimated, for the whole sample and sub-groups
- f) Plots of trajectories of symptoms, grouping patients according to sub-groups, and patterns in changes in symptoms using radar charts and area under the curve.
- g) Modelling to track symptoms and medication (e.g. pain and analgesia, anxiety and anxiolytics, fever and antipyretics etc. etc.) and relationship with variables thought to affect outcome (e.g. comorbidities, age, gender etc.) over time using regression analysis adjusted for confounders and any service clustering.

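### WP1 names only unadjusted chi-squared tables, so a pooled NHS v voluntary comparison can show a service-type difference as a funding difference; compare funding within service type.

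*Protocol*

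**What the plan says.** Section 6.10 (WP1, survey) opens with descriptive analysis. It then allows, if the data support it, "contingency tables assessed using chi-squared to compare types of responses/challenges/use of technology by key characteristics". The examples given are "e.g. of hospital support teams, services that are NHS or voluntary sector funded". The same paragraph also looks for "Hospice and palliative care service characteristics that are associated with most effective changes".

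No stratification, covariate adjustment or model is named for WP1. For WP2, by contrast, sections 6.7 and 6.10 plan regression that accounts for confounders or casemix and for service clustering. The full statistical analysis plan is promised under the WP2 heading of 6.10.

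Section 6.7 says of WP1: "Is largely descriptive yielding rich information". It expects this return: "A response rate at 60%, yields 390 services, ~130 inpatient hospices, 130 hospital palliative care teams, 130 home care teams".

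On how funding relates to service type, section 6.5 lists "voluntary hospices, hospital based palliative care teams, home care/community teams and other services" for WP1 and, for WP2 site recruitment, "20 services across settings (hospital, community, voluntary hospice". The opening of 6.5 also says that specialist units and hospices may be voluntary or managed by the NHS. The protocol gives no table or percentage of funding by type.

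**The concern.** If hospices are more often voluntary and hospital teams more often NHS, then a two-way table of funding against, say, equipment shortage also compares hospices with hospital teams. Shortages, use of technology and redeployment could plausibly differ between those settings whoever pays. A chi-squared test on the pooled table cannot separate the two explanations.

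Objective 3 in section 6.2 asks for facilitating components and barriers, including equipment availability. The aim in 6.1 is rapid clinical and policy guidance, and section 5.4 names the voluntary sector among the services whose best contribution the study should identify. A statement that voluntary-sector services lacked equipment could reach policy readers even if NHS and voluntary services of the same type did not differ.

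**Working it through.** **The plan's own figure.** Section 6.7 says that subgroups above 105 detect an effect size of 0.35 by chi-squared with 5 df, alpha 0.05 and 80% power. Taking the effect size as Cohen's w:

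- The critical value of chi-squared on 5 df is 11.07, and the noncentrality needed for 80% power is 12.83.
- N = 12.83 / 0.35² = 12.83 / 0.1225 = 104.7, rounded up to 105.

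The figure reproduces and is not in question. For a table on 1 df over all 390 services, the noncentrality needed is 7.85, so w = √(7.85 / 390) = 0.14 is detectable with 80% power. A modest confounded difference can therefore reach p<0.05.

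**One worked example.** The 130 services of each type come from section 6.7. The rest is assumed: NHS-funded share 95% of hospital teams, 25% of hospices and 60% of home care teams; a shortage reported by 30%, 60% and 45% of them respectively, whoever funds them.

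- NHS services: 123.5 + 32.5 + 78 = 234. Voluntary: 6.5 + 97.5 + 52 = 156.
- NHS rate: (123.5×0.30 + 32.5×0.60 + 78×0.45) / 234 = 91.65 / 234 = 39.2%.
- Voluntary rate: (6.5×0.30 + 97.5×0.60 + 52×0.45) / 156 = 83.85 / 156 = 53.8%.
- Pooled rate: 175.5 / 390 = 0.45. Standard error: √[0.45×0.55×(1/234 + 1/156)] = 0.0514.
- z = (0.5375 − 0.3917) / 0.0514 = 2.84. The chance of p<0.05 is about P(Z > 1.96 − 2.84) = 81%.

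By construction, funding has no effect within any service type.

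**How the result moves with the assumptions.** Each scenario was simulated 20,000 times with 130 services per type and no funding effect within type. The crude test is the pooled 2×2 chi-squared without continuity correction. The stratified test is Cochran-Mantel-Haenszel by service type. Shares and rates are in the order hospice / hospital / home care, and all are assumed.

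| Voluntary share (%) | Response rate (%) | Apparent voluntary v NHS (%) | Crude p<0.05 | Stratified p<0.05 |
|---|---|---|---|---|
| 33/33/33 | 60/40/50 | 50.0 v 50.0 | 4.9% | 4.9% |
| 60/20/40 | 50/40/45 | 46.7 v 43.9 | 8.4% | 4.8% |
| 60/20/40 | 60/40/50 | 53.3 v 47.8 | 18.9% | 5.1% |
| 80/5/40 | 60/40/50 | 56.0 v 45.7 | 52.1% | 4.9% |
| 70/10/40 | 70/30/50 | 60.0 v 43.3 | 90.8% | 5.0% |
| 80/5/40 | 70/30/50 | 62.0 v 41.4 | 98.4% | 5.0% |

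Over all 20 scenarios run, the crude test rejected in 4% to 5% of runs when funding was unrelated to type, and in 8% to more than 99% when it was related. The stratified test stayed between 4.8% and 5.3%.

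**The case against.** **The comparison is conditional and descriptive.** The tests are run only if the data allow, funding is one example among possible characteristics, and WP1 is described as largely descriptive. No independent effect of funding is claimed. A crude difference is a valid description of how NHS and voluntary services fared. This stands, and it limits the weight of the point. It does not remove it, because the same paragraph seeks characteristics associated with the most effective changes, and the condition governs whether the tests are run, not how.

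**The tables might be made within service type.** Section 6.10 does not say whether they are pooled, and the 105 in section 6.7 is smaller than one service type. Within a type, setting could not confound funding. The text does not exclude this. But the same sentence offers hospital support teams as another comparison characteristic, which makes pooling over types the more natural reading. The wording is at best ambiguous.

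**The link between funding and type is not established.** This also stands. It is suggested by wording only, one of the supporting phrases concerns WP2 sites, and 6.5 says hospices can be NHS managed.

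**Such detail belongs in an analysis plan.** That is often fair, but the plan promised in 6.10 sits under WP2, and for WP1 the protocol itself names the test.

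**A stronger reading to avoid.** A reader might infer that the survey will report a setting difference as a funding difference. The protocol does not support that. It gives no funding shares by type, and under a weak link the false-positive rate is only 8%.

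**Conclusion.** The point holds in a limited form. The protocol names unadjusted chi-squared tables as the only WP1 test, gives funding as a comparison, and says nothing that separates funding from service type. If the two are associated, a pooled table can show a setting difference as a funding difference.

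The numbers rest on assumed funding shares and response rates, so they show what could happen rather than what to expect. The chance of a spurious p<0.05 is about 5% with no link and over 90% with a strong link and a wide gap between settings. The sample size in 6.7 is unaffected. The same argument could be made for region or local COVID-19 burden, but nothing in the protocol allows that to be sized. This is a cheap improvement to the wording of the analysis.

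**What to change.** In section 6.10 (WP1), state that comparisons by funding are made within service type, using a Mantel-Haenszel test stratified by type or a logistic regression that includes type. Keep the pooled chi-squared tables as description, labelled unadjusted. Adjust for region or local COVID-19 burden only if the data are available and the numbers allow.

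Service type and location are among the key survey variables in section 6.9, so stratifying by type needs no new data. Funding source and local COVID-19 burden are not in that list. The sponsor should confirm that funding is captured, since the comparison already named in 6.10 depends on it.

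The statistical cost is wider intervals where a type has few services in one funding group. With the assumed 95% NHS share, only 6 or 7 of 130 hospital teams would be voluntary (130 × 0.05 = 6.5), so that stratum would add little information on funding. A model with many factors for every response would be fragile for the same reason.
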